10.7 METHODS FOR ADDITIONAL ANALYSES

SUBGROUP ANALYSIS: If sample size allows, we will carry out the following pre-specificed subgroup analyses; by IPV type, by severity of IPV, by whether remain with partner, baseline ABI total score, and baseline age.

RECORD LINKAGE: At 24 months with participants' consent, we will apply to the following information systems to conduct 'Names Enquiries' under general processing purposes to check whether our participants appear in their datasets.

- Convictions/arrests for IPV (Health and Justice Information Service; Police National Computer; Prison database)
- Death (Death Register)
- Health/Substance use treatment and prescriptions (National Drug Treatment and Monitoring Service (NDTMS)/ Hospital Episode Statistic (HES) (NHS Digital)/ Scottish Morbidity Record (SMR) (Public Health Scotland))

We will seek approval from relevant Public Benefit and Privacy Panels at the start of the project to avoid delays. This will require a data sharing agreement to be in place between each agency and the sponsor. We will consult with the Data Protection Officer and legal team at King's College London to complete the legal basis documentation. All record linkage will require a data protection impact assessment to be completed and participants' consent. With NDTMS for example, probabilistic sampling will be used for data linkage. The probabilistic linkage model allows for different fields to have higher discriminatory power than others (for example, if 2 records have the same sex, that is less discriminatory for linking purposes than the 2 records having the same set of first name and surname initials). For small data sets, it is possible to compare each record in one data set with each record in another data set, but the software allows us to incorporate 'blocking rules'. This helps us to narrow down the number of record pairs being compared and enhance the efficiency of the linkage. Blocking rules are a set of criteria that any 2 records must meet (for example, initials and dates of birth must match) before any other comparisons are done. In practice, we can develop multiple blocking rules (for example, initials and dates of birth must match or initials and postcodes must match). This approach reduces how many record pairs are compared by discarding implausible matches. For example, if there was one data set with 10,000 records and another with 100,000 records, there are

potentially a billion comparisons that could be made. The blocking rules allow for most of this potential billion to be ignored.

Conducting the probabilistic linkage involves calculating 3 fundamental statistics.

- The m-probability is the likelihood that 2 records match on a given field, if the records are a true match (the records belong to the same person).
- The u-probability is the likelihood that 2 records match on a given field, if the records are a false match (the records belong to different people).
- Lamda is the overall probability that any 2 randomly selected records are a match. We can then apply Bayes' formula to assign a single probability that each pair of records is related to the same individual across the 2 systems.

Splink is a Python package designed to implement the Fellegi-Sunter algorithm at scale. This is implemented on a secure partition of UKHSA's network (where NDTMS is also stored) with limited personnel access.

Other data linkage will be conducted using participants full name.

PROCESS EVALUATION: Context, fidelity, dose delivered, dose received, reach and recruitment for ADVANCE-D will be evaluated. 88 Longitudinal qualitative interviews (at 4- and 12- months) with 40 men receiving ADVANCE-D and their (ex)-partners and with staff post intervention will provide in-depth understanding of mechanisms of action, how context affects implementation, engagement, and behaviour change.

ANALYSIS OF RECORD LINKAGE: A long term follow-up will be carried out at 24-month via record linkage. This analysis will be described in the SAP and assess recidivism (criminal justice data), mortality (via Office for National Statistics), drug treatment (via NDTMS/SMR), prescription (NHS Digital/Public Health Scotland) and hospital admission data (via HES/SMR). Mortality will be analysed with a multi-level logistic regression in a similar manner to the primary outcome.

ECONOMIC EVALUATION: A senior health economist will oversee the analysis conducted by the trial health economist. An economic evaluation will be embedded within the study to compare ADVANCE-D with usual CJOM. The costs of providing ADVANCE-D and usual CJOM will be recorded prospectively and include the cost of staff time, training, overheads and consumables. We will first use clusters as the costing unit to calculate an intervention delivery cost per cluster. Once the treatment ends, we will assign the cluster costs proportionally to each participant according to their attendance. This will result in an intervention delivery cost per participant and reflect variance among participants. Quantities of resources used will be collected alongside the study and local unit costs will be applied to derive the cost per participant in treatment condition. This will provide a costing of the interventions with a per patient cost attached. Health care utilisation data for contacts with NHS primary care, secondary care, personal social services (PSS), will be collected using a SUQ by self-report at each follow up. The published secondary sources of unit costs of these services of the appropriate year⁸⁹⁻⁹¹ will be applied to the quantities up to form the costs from the NHS/PSS perspective⁹². We will collect resource use outside of the NHS/PSS domain (criminal justice contacts, legal aid, housing service, productivity losses) using the SUQ via self-report, and apply national average costs to these quantities to derive patient cost outside of the NHS/PSS perspective. Incidents of IPV will be collected in the SUQ. The aggregate costs in each category will be presented as part of the cost-consequences analysis. Secondary care contacts are taken from the record linkage with HES. Quantities recorded are multiplied by national average unit costs for health care and criminal justice contacts to derive cost profiles for all participants. Study participants will also complete EQ-5D-5L at baseline and each follow up and we will calculate QALYs using the area under the curve. 91 We will use the tariff as recommended by NICE at the time of analysis to derive health related quality of life (HRQoL) utility scores from the EQ-5D-5L data. 92 Participant costs (intervention and NHS/PSS costs) 89.90 are combined with QALYs to estimate the incremental cost per QALY of the intervention over and above CJOM at follow up. Underlying uncertainty around the decision to adopt the intervention is assessed using non-parametric bootstrap re-sampling. Bootstrapping is an efficient method for calculating the confidence limits for the incremental cost effectiveness ratio (ICER) as its validity does not depend on any specific form of underlying distribution. We perform 5000 replications and construct the 95% CI for the ICERs based on the

bootstrapping results. Cost-effectiveness acceptability curves (CEAC) will be constructed based on the bootstrap iterations⁹³ to estimate the probability that the intervention is cost-effective at different threshold values for one QALY gain. A range of sensitivity analyses will be conducted to test the robustness of the results under different scenarios, including probabilistic sensitivity analyses. In the main analysis, missing data will be imputed using Rubin's multiple imputation method.⁹⁴ As part of the sensitivity analysis, we conduct an additional set of analyses using the complete case analysis consistent with the statistical analysis, whereby results are analysed only for those participants who had both the completed cost and outcome data at the same time. Given the range of stakeholders involved and the multiplicity of cost and outcome domains the study results will be presented as a cost-consequences analysis (CCA) in addition to the CEA from the NHS/PSS perspective following the NICE guidance. Costs to the NHS and PSS, the criminal justice system and wider society will be reported in a disaggregated form to enable each stakeholder to understand the impact of ADVANCE-D on their budget when compared to the usual care intervention.

QUALITATIVE ANALYSIS: Standards for Reporting Qualitative Research (SRQR) will be followed when analysing the qualitative research. 95 Multiple perspectives data (i.e., from couples (dyads) and intervention staff) will be collected with brief semi-structured interviews at three points in a qualitative longitudinal process evaluation. Interviews will be audio recorded and transcribed verbatim. To expedite the management and analysis of longitudinal data, techniques from rapid data analysis ⁹⁶ will involve researchers transferring summaries of responses and fieldnote reflections directly into a matrix that corresponds to the three semi-structured interview schedules for each group to be interviewed. Summarised data will be entered into frameworks composed of three excel spreadsheets (one sheet for each interview), in which each column is titled with the topic guide questions. Data for each time point interview and category of interviewee will then be merged into a single framework that will enable comparison, interpretation, and synthesis of longitudinal data. Codes will be developed and refined, and thematically analysed. Data for each time point interview and category of interviewee will then be merged into a single framework that will enable comparison, interpretation, and synthesis of longitudinal data. Data will be managed using Nvivo. The five steps of the framework approach will be used for analysis: familiarization; identifying a thematic framework; indexing; charting; and mapping and interpretation. 97 Coding will be attentive to contradictions and tensions within and between men's, (ex)-partners and practitioners' accounts of behaviour change. The COREO (Consolidated criteria for Reporting Qualitative research) Checklist will be followed when analysing and reporting the qualitative research. 98 Interviews with men and (ex)-partners will be conducted by different researchers to avoid inadvertent information sharing. 99 Five researchers will code and analyse interviews, under the supervision of qualitative research co-applicant.

TRIANGULATION: The integration of qualitative and quantitative process data with study outcomes will help understand the study findings. The results from the process evaluation and changes in outcomes will be triangulated into an overall analysis and interpretation of key implementation lessons, presented as a strengths, weaknesses, opportunities, and threats (SWOT) analysis.⁹⁹ The Standards for Reporting Qualitative Research (SRQR)⁹⁵ will be followed when analysing the qualitative research. Focus groups and semi-structured interviews will be conducted by phone or video call, digitally recorded and transcribed verbatim. Data will be organized and coded using Nvivo. Multiple coders will enhance the rigour of the analysis.

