Healthcare costs are 42% higher for IPV survivors, persisting for years after IPV stops.⁵³ IPV costs the lives of almost 2 UK women a week.⁵⁴ Social and economic costs of IPV are around £66bn a year in the UK.⁵⁵ In the UK, perpetrator programmes reduce IPV by 30-65%, ^{56,57} an investment return of £14 for every £1 spent.⁵⁶ Annually illicit drug use costs £20bn.⁵⁸ Every £1 spent on drug treatment saves £4 to society.⁵⁸ It costs £44,600 a year to imprison someone.⁵⁹ Therefore, providing targeted perpetrator programmes to court-mandated offenders who misuse substances and are ineligible for existing perpetrator programmes will result in reduced costs to society, health and social care and improved well-being of men, their (ex)-partners and children. If (cost) effective, ADVANCE-D would reduce recidivism and future imprisonment and could be implemented across the UK and wider.

What works to reduce IPV by men with substance use problems

Reviews of IPV perpetrator interventions for men have shown mixed results and small effect sizes. ^{23,33,37,38,41-43} Perpetrator programmes can be effective in reducing IPV, as a meta-analysis of 13 studies has illustrated, (pooled estimate = -0.85; 95% CI -1.02 to -0.69). ⁴³ The authors found better outcomes when interventions addressed, substance abuse or trauma components (substance abuse: CI = -3.20 to -1.08 and trauma: CI = -2.63 to -0.30). Our review of voluntary and court-mandated interventions to reduce IPV among men with substance use problems, ³⁷ highlighted both the small number of trials and short duration of follow-up. Overall, the results of a small number of individual trials demonstrated some reductions in IPV outcomes in the short term - up to 3 months post treatment.

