3. PARTICIPANTS

3.1 STUDY SETTING & RECRUITMENT

Courts mandate sentences to men convicted of IPV. Sentences include a rehabilitation activity requirement (RAR) in England; or a community payback order (CPO) in Scotland. These requirements/orders are given with a view to promoting the offender's rehabilitation and reduce the likelihood of reoffending. Men must see a Probation Practitioner (PP) at a Probation Delivery Unit (PDU; England)/ Justice Social Worker (JSW) at a Justice Social Work team (JSWT; Scotland) within 5 days post sentencing when sentence planning will take place. PDU/ JSW team make decisions on the offender management required to address any support recommended by court. Alongside the RAR or CPO, men will have a supervising PP/ JSW to monitor compliance to the community sentences. Any violation of conditions will be referred back to court.

There are 11 probation regions in England. PDU are the local units in each of these probation regions. For example, Greater Manchester (probation region) has 9 local PDU (see Table 1). Scotland has 32 Justice Social Work areas (JSW area) that provide statutory criminal justice services in JSWT. For example, City of Edinburgh (JSW area) has 2 local JSW teams (see Table 1). PDU and JSWT will be treated as clusters for the purpose of the trial.

To be eligible to take part in the trial, PDU and JSWT must have a central intervention delivery model (e.g. a central intervention delivery team in Greater Manchester deliver interventions across all 9 PDU); have trained and certified facilitators and partner support workers; and not be sites in other intervention trials. Facilitators in each Probation Region (England) and JSW area (Scotland) will be trained to centrally deliver the ADVANCE-D Programme and will be blind to allocation of PDU/ JSWT. Each PDU/ JSWT will recruit and consent 14 men to the trial before the outcome of allocation is known to them.

A total of 32 PDU/ JSWT are required for the cRCT. Twelve PDU/ JSWT (clusters) from the 24 clusters in Table 1 will be allocated at random for men to receive the ADVANCE-D Programme delivered by a central team + usual community justice offender management (CJOM) (Option 1) OR usual CJOM (Option 2) during the internal pilot from two probation regions from England (Greater Manchester and the North West) and one JSWT from Scotland (City of Edinburgh). An additional 20 PDU/ JSWT will be recruited to the main trial.

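### The only specified cost per QALY is labelled NHS/PSS but includes ADVANCE-D delivery cost, which falls largely on probation and justice social work staff, and leaves out criminal justice contact costs

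*Protocol*

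**What the plan says.** All of the economic methods are in Protocol section 10.7, under Economic evaluation.

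- **Numerator.** The costs entering the ratio are "Participant costs (intervention and NHS/PSS costs", and these "are combined with QALYs to estimate the incremental cost per QALY of the intervention over and above CJOM at follow up". The bootstrap interval and the cost-effectiveness acceptability curve (CEAC) are built on this ratio.
- **Label.** The cost-consequences analysis (CCA) is presented "in addition to the CEA from the NHS/PSS perspective following the NICE guidance".
- **Criminal justice costs.** "We will collect resource use outside of the NHS/PSS domain (criminal justice contacts, legal aid, housing service, productivity losses" is how the section introduces these items. They are valued at national average costs, and "The aggregate costs in each category will be presented as part of the cost-consequences analysis". On reporting: "Costs to the NHS and PSS, the criminal justice system and wider society will be reported in a disaggregated form".
- **Delivery.** Section 3.1 states: "Facilitators in each Probation Region (England) and JSW area (Scotland) will be trained to centrally deliver the ADVANCE-D Programme". The training paragraph in section 4.1.2 requires three trained probation officers per PDU.
- **Expected value.** Section 1.1 expects less recidivism and imprisonment if the programme works, and gives a unit cost: "It costs £44,600 a year to imprison someone".

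Section 10.7 specifies no second ICER or CEAC. It names complete-case and probabilistic sensitivity analyses and refers generally to other scenarios, but names no alternative perspective.

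**The concern.** A cost per QALY is interpretable when its numerator matches a stated budget or group of budgets. Here the label is NHS/PSS, but one component is the cost of a programme run largely by probation and JSW staff. If the numerator is to cover the justice sector's spending on the programme, it should also cover that sector's other costs, which may move in either direction as a result. The stated numerator does the first and not the second.

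At stake is the reading of the ICER, its bootstrap interval and the CEAC, the outputs that section 10.7 ties to the adoption decision. Section 1.1 places much of the expected economic benefit in criminal justice, and that is the component these outputs leave out.

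**Working it through.** The plan gives no economic figure to reproduce, so the check traces each cost category and then uses simple arithmetic to show how the omission acts.

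**1. Where each category goes (section 10.7 unless noted)**

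| Cost | Sector | In the ICER? | In the CCA? |
|---|---|---|---|
| ADVANCE-D delivery (staff time, training, overheads, consumables) | Largely probation/JSW by inference (3.1, 4.1.2); partner support from women's services (3.4.15); website managed by an NHS provider (4.1.1) | Yes | Yes |
| Usual CJOM delivery | Probation/JSW | Recorded; may be netted off in the increment | Yes |
| NHS and personal social services | NHS/PSS | Yes | Yes |
| Criminal justice contacts | Outside NHS/PSS by the plan's own classification | No | Yes |

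**2. Algebra.** Write ΔD for the difference in delivery cost per man (net of usual CJOM), ΔH for NHS/PSS cost, ΔJ for criminal justice contact cost, ΔQ for QALYs (taken as positive) and λ for the value of a QALY.

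- Plan: ICER = (ΔD + ΔH) / ΔQ
- Public sector: ICER = (ΔD + ΔH + ΔJ) / ΔQ
- Public sector minus plan = ΔJ / ΔQ
- On the net benefit scale, λΔQ minus cost, public sector minus plan = −ΔJ, whatever ΔQ and λ are

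If contact costs fall (ΔJ < 0), the plan's ICER is too high against the public-sector view. If they rise (ΔJ > 0), it is too low. If ΔJ = 0, the two agree.

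**3. Illustration.** The only figure from the document is £44,600 per prison year (section 1.1). Delivery cost, days averted and QALY gain are assumed, and ΔH is set to 0.

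- Custody per day: 44,600 / 365 = £122.19
- Break-even days averted per man = ΔD / 122.19: £1,000 gives 8.2; £2,000 gives 16.4; £3,000 gives 24.6

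With ΔD = £2,000 and ΔQ = 0.02:

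| Custody days averted per man | Plan's ICER | Adding custody saving |
|---|---|---|
| 0 | 2,000 / 0.02 = £100,000 | £100,000 |
| 10 | £100,000 | (2,000 − 1,221.92) / 0.02 = £38,904 |
| 20 | £100,000 | (2,000 − 2,443.84) / 0.02 < 0, a net saving |

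For 10 days averted, the shift in the ICER depends heavily on the assumed QALY gain: 1,221.92 / 0.05 = £24,438 and 1,221.92 / 0.01 = £122,192 per QALY. On the net benefit scale the same 10 days is £1,222 per man throughout.

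**The case against.** The strongest reply is that the plan already deals with several sectors through the CCA. That is the only economic analysis named in the objectives (section 2.2), and it reports justice costs separately so that each stakeholder can see the effect on its own budget. The ICER's contents are stated openly, and further perspectives can be set out in an analysis plan. Much of this stands: the information is not lost, and the matter is secondary. But disaggregated reporting does not enter the ICER, its bootstrap interval or the CEAC, and the label and numerator are fixed in the protocol, not deferred.

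Other limits also stand. No section says who pays for delivery; probation/JSW is an inference from who the facilitators are, and partner support and the website lie elsewhere. Usual CJOM cost is recorded too, so what is missing is contact costs, not every justice cost.

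Three stronger readings are tempting and are not supported:

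- **That the programme could be found not cost-effective by construction.** No threshold or decision rule is fixed; the CEAC covers a range of values. The direction depends on an unknown effect on re-offending, and section 1.1 itself cites a meta-analysis finding insufficient evidence that court-mandated programmes reduce re-assault.
- **That custody cost is already collected in the service use questionnaire (SUQ).** Sections 3.7.6 and 10.7 name criminal justice contacts, not custody. A prison database appears only in the 24-month linkage (sections 3.7.9 and 10.7), and the costing text uses linkage only for hospital care.
- **That a true NHS/PSS ICER must leave out delivery cost.** The documents do not establish this, and a ratio without the programme's own cost would say little about adopting it.

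**Conclusion.** The point holds as a mismatch between label and numerator, with a real but unquantified consequence. The only specified cost per QALY counts much of the justice sector's delivery outlay, net of any usual CJOM cost, without that sector's contact costs, and so corresponds to no single stated perspective. This rests on two readings: that delivery by probation and JSW staff means that sector bears most of the delivery cost, and that criminal justice contacts are confined to the CCA, as section 10.7 indicates.

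The protocol cannot settle the size or the sign. The custody figures show only that modest differences in custody time could change the ratio materially; they do not estimate what the trial will find. This is a worthwhile correction to a secondary analysis and does not affect the primary outcome or the CCA.

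**What to change.** In section 10.7:

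1. Label the present ICER and CEAC as intervention plus NHS/PSS costs, and state which sector or sectors bear the delivery cost, including partner support and the website.
2. Pre-specify beside it, as a secondary analysis, a public-sector incremental net benefit and CEAC that add the criminal justice contact costs collected in the SUQ. Net benefit is preferable to a second ratio because it does not depend on dividing by a small QALY gain. State that supervision already costed as CJOM delivery is not counted again as a contact.
3. Confirm whether the SUQ captures time in custody. If it does not, say so and state whether custody will be costed from another source.

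For contacts already collected and valued, this needs wording and one further run of the same analysis. Custody may need more, depending on the answer to item 3. The downside is a second set of cost-effectiveness results to report; naming it in advance avoids choosing a perspective after the results are known.
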